5.3. Lifestyle Consideration

5.3.1. Dietary and Other Restrictions

- Grapefruit and Seville oranges and their juices can inhibit CYP3A4 and should not be consumed excessively while on study.
- Subjects should be cautioned to avoid sun exposure and take appropriate protective precautions.
- Because of the potential for reproductive adverse effects, options for sperm and egg banking should be discussed with the subject, if appropriate.
- Subjects should be provided loperamide at the first dosing visit, instructed on its use and counseled to contact their clinician at the first occurrence of diarrhea or loose stools.
- Because of the potential for Notch-related effects on gastrointestinal mucosa, gastric ulcer prophylaxis (e.g. with a proton pump inhibitor) should be considered for all subjects.

Refer to the AL101 IB for further information.

5.4. Subject Identification

Each subject who signs informed consent will be assigned a subject number via the Interactive Web/Voice Response System (IXRS). This number will be used as the primary identification for the complete duration of the study. After the subject signed the informed consent form (ICF), the investigator will enter the subject into the Screening section of the electronic case report form (eCRF).

5.5. Screen Failures

Screen failures are defined as subjects who consent to participate in the clinical study but are not subsequently entered in the study. A minimal set of screen failure information is required to ensure transparent reporting of screen failure subjects to meet the Consolidated Standards of Reporting Trials (CONSORT) publishing requirements and to respond to queries from regulatory

authorities. Minimal information includes demography, screen failure details, eligibility criteria, and any SAE.

Re-screening/re-assessment outside the Screening period will be possible on a case-by-case basis following Sponsor approval. Subjects allowed to be re-screened will be assigned a new screening number (with referral in eCRF to the previous screening number); such subjects will be determined a screen failure after the second screening confirmed the subject is ineligible.

6. INVESTIGATIONAL PRODUCT AND CONCOMITANT THERAPY

Investigational product is defined as any investigational intervention(s), marketed product(s), placebo, or medical device(s) intended to be administered to a study subject according to the study protocol.

6.1. Investigational Product Administered

AL101 is a potent and selective inhibitor of gamma secretase-mediated Notch signaling.

Table 2 Investigational product

Intervention Name	AL101
Type	Small Molecule
Dose Formulation	Solution for infusion
Unit Dose Strength(s)	1.2 mg/mL
Dosage Level(s)	4 or 6 mg (1.2 mg/mL x 5mL) (refer to Figure 1 and Section 4.1 for dose determination) Frequency: Weekly (QW) on Days 1, 8, 15 and 22 of each 28-day cycle
Route of Administration	AL101 will be administered using an IV infusion pump over 60 minutes; time windows of -5 minutes to +15 minutes are permitted. The connection between the tubing from the infusion pump to the subject should be close to the insertion of the intravenous catheter. The exact duration of infusion should be recorded in both source documents and eCRFs. The start time of dose administration will be called “0” hour. If an infusion is extended, interrupted or discontinued prior to completion, the duration and the reason for any dose extension, interruption or discontinuation will be recorded in the eCRF.
Preparation	Prior to IV administration, the AL101 6 mg (1.2 mg/mL x 5mL) is diluted in a 250 mL infusion bag of 0.9% Sodium Chloride Injection, USP (normal saline) or 5% Dextrose Injection, USP (D5W). Only diethylhexyl phthalate-free bags and infusion sets can be used to administer solutions. Aseptic practices should be followed when handling, preparing, and administering the infusion solutions because the drug vial does not contain antibacterial preservatives or bacteriostatic agents. A sufficient excess of drug product is included in each vial to account for withdrawal losses. Refer to Study Pharmacy Manual for more details.
IMP definition	A new drug that is used in a clinical investigation (FDA)
Sourcing	AL101 is manufactured by Bristol-Myers Squibb. Investigational product will be provided to the site centrally by the Sponsor or designated representative (Fisher Clinical Services, USA).

Intervention Name	AL101
Packaging and Labeling	
AL101 is supplied as a single-use sterile solution 5 mL per vial (1.2 mg/mL; equivalent of 6 mg per vial) for IV administration; The secondary packaging and labeling of IP will be performed by Fisher Clinical Services.
 
All packaging and labeling operations for IP will be performed according to Good Manufacturing Practices for Medicinal Products and the relevant regulatory requirements. Label text for the AL101 vial will at a minimum include the protocol number, the contents of the vial, batch number, storage conditions, and Sponsor name and address.

Former Name(s) or Alias(es)]	BMS-906024

6.2. Handling, Storage and Accountability

1. The investigator or designee must confirm appropriate temperature conditions have been maintained during transit for IP received and any discrepancies are reported and resolved before use of IP.
2. Only subjects enrolled in the study may receive IP and only authorized site staff may supply or administer IP. All IP must be stored in a secure, environmentally controlled, and monitored (manual or automated) area in accordance with the labeled storage conditions with access limited to the investigator and authorized site staff.
3. The investigator, institution, or the head of the medical institution (where applicable) is responsible for IP accountability, reconciliation, and record maintenance (i.e., receipt, reconciliation, and final disposition records).
4. At the end of the study, the monitor will conduct a final drug reconciliation for all subjects and the study site overall. All records of IP administration, accountability records and IP disposition records will be examined and reconciled by the study monitor. Further details will be provided in the Study Pharmacy Manual.

Further guidance and information for the final disposition of unused IP are provided in the Pharmacy Manual.

6.3. Compliance of Investigational Product

When subjects are dosed at the site, they will receive IP directly from the investigator or designee, under medical supervision. The date and time of each dose administered in the clinic will be recorded in the source documents and recorded in the eCRF. The dose of IP and study subject identification will be confirmed at the time of dosing by a member of the study site staff other than the person administering the IP.

6.4. AL101 Dose Modification and Toxicity Management Guidelines

Dose modification associated with AL101 is described below in [Table 3](#).

The causality assessment (related/not related) as defined in Section 10.3.4 will be used by the investigator for assessing drug-related non-hematological Grade 3 (except isolated Grade 3 electrolyte abnormality that are not associated with clinical signs or symptoms and are reversed with appropriate medical intervention within 48 hours) and hematological Grade 4 toxicities. If there is a relationship to the drug, this will lead to a 1 dose level reduction for AL101. For easily manageable Grade 1 or 2 toxicity, no dose reductions are required, but careful observation and treatment is required. Dose modification of intolerable Grade 2 toxicity will be evaluated on a case-by-case basis with the Sponsor. Re-escalation of the dose following a dose reduction is not allowed, however, subject can be re-treated at the lower dose. The subject can resume treatment with AL101 after resolution of signs and symptoms to Grade 1 or a baseline level (whichever is greater) at the discretion of the investigator. Maximum AL101 treatment interruption allowed is 28 days; treatment interruption longer than 28 days will result in discontinuation of subject from the study. Additional treatment guidelines may be implemented by the investigators, with agreement of the Sponsor/Medical Monitor, as needed to ensure subject safety.

Table 3 Dose Modification Criteria for AL101

Dose Modification Criteria for AL101 -Related Adverse Events	AL101 modification at next dose	
	Dose 6 mg QW	Dose 4 mg QW
Grade 4 neutropenia lasting \geq 7 days	Decrease AL101 dose to 4 mg QW for first episode and to 2.4 mg QW for second episode.	Decrease AL101 dose to 2.4 mg QW
Grade 3 or 4 febrile neutropenia	Decrease AL101 dose to 4 mg QW for first episode and to 2.4 mg QW for second episode.	Decrease AL101 dose to 2.4 mg QW
Grade 4 thrombocytopenia or \geq Grade 3 thrombocytopenia with significant bleeding	Decrease AL101 dose to 4 mg for first episode and to 2.4 mg QW for second episode	Decrease AL101 dose to 2.4 mg QW
Grade 1 diarrhea	
No change in AL101 dose.
 
Guidelines for the management of diarrhea:
 
 • Loperamide 4 mg at the first onset of diarrhea, then 2 mg every 2 hours around-the-clock until diarrhea free for at least 12 hours. Subjects may take loperamide 4 mg every 4 hours during the night. These doses should not be used for more than 48 hours due to the risk of paralytic ileus. • For subjects that cannot tolerate loperamide or do not get adequate relief with maximum doses, standard doses of LOMOTIL® (diphenoxylate/atropine) may be added or used instead of loperamide. • Additional antidiarrheal measures, such as octreotide, may be used at the discretion of the investigator or treating physician. 	
No change in AL101 dose.
 
Guidelines for the management of diarrhea:
 
 • Loperamide 4 mg at the first onset of diarrhea, then 2 mg every 2 hours around-the-clock until diarrhea free for at least 12 hours. Subjects may take loperamide 4 mg every 4 hours during the night. These doses should not be used for more than 48 hours due to the risk of paralytic ileus. • For subjects that cannot tolerate loperamide or do not get adequate relief with maximum doses, standard doses of LOMOTIL® (diphenoxylate/atropine) may be added or used instead of loperamide. • Additional antidiarrheal measures, such as octreotide, may be used at the discretion of the investigator or treating physician.
Grade 2 diarrhea	Guidelines for the management of diarrhea:	Guidelines for the management of diarrhea:

Dose Modification Criteria for AL101 -Related Adverse Events	AL101 modification at next dose	
	Dose 6 mg QW	Dose 4 mg QW
	
 Evaluate subject carefully including laboratory assessments (chemistry, liver function tests and lipase) Loperamide 4 mg at the first onset of diarrhea, then 2 mg every 2 hours around-the-clock until diarrhea free for at least 12 hours. Subjects may take loperamide 4 mg every 4 hours during the night. These doses should not be used for more than 48 hours due to the risk of paralytic ileus. For subjects that cannot tolerate loperamide or do not get adequate relief with maximum doses, standard doses of LOMOTIL® (diphenoxylate/atropine) may be added or used instead of loperamide. Additional antidiarrheal measures, such as octreotide, may be used at the discretion of the investigator or treating physician 
If the above measures have not worked, or subject has progressed to Grade 2, or after Grade 1 with no improvement within 3 days with maximum doses of loperamide:
 
 Subject may be treated with dexamethasone at a dose of 8 mg every 8 hours (Q8h) for up to 5 days. If still no improvement in symptoms, the subject may continue with the dexamethasone or consider switching to budesonide 9 mg once daily (QD). Refer to Section 6.6.2 for additional instructions on premedication with steroids. 	
 Evaluate subject carefully including laboratory assessments (chemistry, liver function tests and lipase) Loperamide 4 mg at the first onset of diarrhea, then 2 mg every 2 hours around-the-clock until diarrhea free for at least 12 hours. Subjects may take loperamide 4 mg every 4 hours during the night. These doses should not be used for more than 48 hours due to the risk of paralytic ileus. For subjects that cannot tolerate loperamide or do not get adequate relief with maximum doses, standard doses of LOMOTIL® (diphenoxylate/atropine) may be added or used instead of loperamide. Additional antidiarrheal measures, such as octreotide, may be used at the discretion of the investigator or treating physician 
If the above measures have not worked, or subject has progressed to Grade 2, or after Grade 1 with no improvement within 3 days with maximum doses of loperamide:
 
 Subject may be treated with dexamethasone at a dose of 8 mg Q8h for up to 5 days. If still no improvement in symptoms, the subject may continue with the dexamethasone or consider switching to budesonide 9 mg QD. Refer to Section 6.6.2 for additional instructions on premedication with steroids.

Dose Modification Criteria for AL101 -Related Adverse Events	AL101 modification at next dose	
	Dose 6 mg QW	Dose 4 mg QW
	
Dose modifications for AL01:
 
Interrupt AL101 until resolution to \leq Grade 1 (refer to Section 6.4.2 and above for management guidelines for diarrhea).
 
Change dose regimen to 6 mg 2 weeks on / 1 week off for first episode
 
Decrease AL101 dose to 4 mg QW for second episode and to 2.4 mg QW for third episode.
 
If the diarrhea does not resolve to Grade 1 by 14 days, the subject will be discontinued from IP (refer to Section 7.2 for handing IP discontinuation).
 
If treatment interruption is longer than 28 days, the subject will be discontinued from IP (refer to Section 7.2 for handing IP discontinuation).
	
Dose modifications for AL01:
 
Interrupt AL101 until resolution to \leq Grade 1 (refer to Section 6.4.2 and above for management guidelines for diarrhea).
 
Decrease AL101 dose to 2.4 mg QW.
 
If the diarrhea does not resolve to Grade 1 by 14 days, the subject will be discontinued from IP (refer to Section 7.2 for handing IP discontinuation).
 
If treatment interruption is longer than 28 days, the subject will be discontinued from IP (refer to Section 7.2 for handing IP discontinuation).

Grade 3 diarrhea	
Guidelines for the management of diarrhea:
 
 Evaluate subject carefully including laboratory assessments (chemistry, liver function tests and lipase) Loperamide 4 mg at the first onset of diarrhea, then 2 mg every 2 hours around-the-clock until diarrhea free for at least 12 hours. Subjects may take loperamide 4 mg every 4 hours during the night. These doses should not be used for more than 48 hours due to the risk of paralytic ileus. For subjects that cannot tolerate loperamide or do not get adequate relief with maximum doses, standard doses of LOMOTIL® 	
Guidelines for the management of diarrhea:
 
 Evaluate subject carefully including laboratory assessments (chemistry, liver function tests and lipase) Loperamide 4 mg at the first onset of diarrhea, then 2 mg every 2 hours around-the-clock until diarrhea free for at least 12 hours. Subjects may take loperamide 4 mg every 4 hours during the night. These doses should not be used for more than 48 hours due to the risk of paralytic ileus. For subjects that cannot tolerate loperamide or do not get adequate relief with maximum doses, standard doses of LOMOTIL®

Dose Modification Criteria for AL101 -Related Adverse Events	AL101 modification at next dose	
	Dose 6 mg QW	Dose 4 mg QW
	
(diphenoxylate/atropine) may be added or used instead of loperamide.
 
 Additional antidiarrheal measures, such as octreotide, may be used at the discretion of the investigator or treating physician 
If the above measures have not worked, or subject has progressed to Grade 3:
 
 Treat with dexamethasone at a dose of 8 mg Q8h for up to 5 days. If still no improvement in symptoms, the subject may continue with the dexamethasone or consider switching to budesonide 9 mg QD. Refer to Section 6.6.2 for additional instructions on premedication with steroids. 
Dose modifications for AL01:
 
Interrupt AL101 until resolution to \leq Grade 1 (refer to Section 6.4.2 and above for management guidelines for diarrhea).
 
Change dose regimen to 6 mg 2 weeks on / 1 week off for the first episode.
 
Decrease AL101 dose to 4 mg QW for second episode and to 2.4 QW mg for third episode.
 
If the diarrhea does not resolve to Grade 1 by 14 days, the subject will be discontinued from IP (refer to Section 7.2 for handling IP discontinuation).
 
If treatment interruption is longer than 28 days, the subject will be discontinued from IP (refer to Section 7.2 for handling IP discontinuation).
	
(diphenoxylate/atropine) may be added or used instead of loperamide.
 
 Additional antidiarrheal measures, such as octreotide, may be used at the discretion of the investigator or treating physician 
If the above measures have not worked, or subject has progressed to Grade 3:
 
 Treat with dexamethasone at a dose of 8 mg Q8h for up to 5 days. If still no improvement in symptoms, the subject may continue with the dexamethasone or consider switching to budesonide 9 mg QD. Refer to Section 6.6.2 for additional instructions on premedication with steroids. 
Dose modifications for AL01:
 
Interrupt AL101 until resolution to \leq Grade 1 (refer to Section 6.4.2 and above for management guidelines for diarrhea).
 
Decrease AL101 dose to 2.4 mg QW.
 
If the diarrhea does not resolve to Grade 1 by 14 days, the subject will be discontinued from IP (refer to Section 7.2 for handling IP discontinuation).
 
If treatment interruption is longer than 28 days, the subject will be discontinued from IP (refer to Section 7.2 for handling IP discontinuation).

Grade 4 diarrhea	Guidelines for the management of diarrhea:	Guidelines for the management of diarrhea:

Dose Modification Criteria for AL101 -Related Adverse Events	AL101 modification at next dose	
	Dose 6 mg QW	Dose 4 mg QW
	
 Evaluate subject carefully including laboratory assessments (chemistry, liver function tests and lipase) Loperamide 4 mg at the first onset of diarrhea, then 2 mg every 2 hours around-the-clock until diarrhea free for at least 12 hours. Subjects may take loperamide 4 mg every 4 hours during the night. These doses should not be used for more than 48 hours due to the risk of paralytic ileus. For subjects that cannot tolerate loperamide or do not get adequate relief with maximum doses, standard doses of LOMOTIL® (diphenoxylate/atropine) may be added or used instead of loperamide. Additional antidiarrheal measures, such as octreotide, may be used at the discretion of the investigator or treating physician Treat with dexamethasone at a dose of 8 mg every Q8h for up to 5 days. If still no improvement in symptoms, the subject may continue with the dexamethasone or consider switching to budesonide 9 mg QD. Refer to Section 6.6.2 for additional instructions on premedication with steroids. 
If the above measures have not worked, or subject has progressed to Grade 4, consult GI as necessary to evaluate for colitis.
 
Dose modifications for AL01:
	
 Evaluate subject carefully including laboratory assessments (chemistry, liver function tests and lipase) Loperamide 4 mg at the first onset of diarrhea, then 2 mg every 2 hours around-the-clock until diarrhea free for at least 12 hours. Subjects may take loperamide 4 mg every 4 hours during the night. These doses should not be used for more than 48 hours due to the risk of paralytic ileus. For subjects that cannot tolerate loperamide or do not get adequate relief with maximum doses, standard doses of LOMOTIL® (diphenoxylate/atropine) may be added or used instead of loperamide. Additional antidiarrheal measures, such as octreotide, may be used at the discretion of the investigator or treating physician Treat with dexamethasone at a dose of 8 mg Q8h for up to 5 days. If still no improvement in symptoms, the subject may continue with the dexamethasone or consider switching to budesonide 9 mg QD. Refer to Section 6.6.2 for additional instructions on premedication with steroids. 
If the above measures have not worked, or subject has progressed to Grade 4, consult GI as necessary to evaluate for colitis.
 
Dose modifications for AL01:


Dose Modification Criteria for AL101 -Related Adverse Events	AL101 modification at next dose	
	Dose 6 mg QW	Dose 4 mg QW
	Permanently discontinue IP (refer to Section 7.2 for handing IP discontinuation)	Permanently discontinue IP (refer to Section 7.2 for handing IP discontinuation)
Grade 2 Diagnosed or suspected clinically significant GI bleeding or unexplained drop in hemoglobin	
Interrupt AL101, perform appropriate diagnosis and treatment.
 
If GI bleeding is considered related to AL101, decrease AL101 to 4 mg QW for first episode and to 2.4 mg QW for second episode.
 
If colitis is suspected, please refer to Section 6.4.3.1, Table 4 for management guidelines for colitis).
 
If treatment interruption is longer than 28 days, the subject will be discontinued from IP (refer to Section 7.2 for handing IP discontinuation)..
	
Interrupt AL101, perform appropriate diagnosis and treatment.
 
If GI bleeding is considered related to AL101, decrease AL101 to 2.4 mg QW.
 
If colitis is suspected, please refer to Section 6.4.3.1, Table 4 for management guidelines for colitis).
 
If treatment interruption is longer than 28 days, the subject will be discontinued from IP (refer to Section 7.2 for handing IP discontinuation)..

Grade 3 or 4 gastric hemorrhage	Permanently discontinue AL101 (refer to Section 7.2 for handing IP discontinuation)	Permanently discontinue AL101 (refer to Section 7.2 for handing IP discontinuation)
QTcF > 500 msec confirmed by at least one repeat ECG and at least 50 msec above baseline	
Interrupt AL101 if needed to optimize electrolyte management.
 
If persists after electrolyte optimization (including dose modification of AL101 if necessary), discontinue IP (refer to Section 7.2 for handing IP discontinuation).
 
If treatment interruption is longer than 28 days, the subject will be discontinued from IP (refer to Section 7.2 for handing IP discontinuation)..
	
Interrupt AL101 if needed to optimize electrolyte management.
 
If persists after electrolyte optimization (including dose modification of AL101 if necessary), discontinue IP (refer to Section 7.2 for handing IP discontinuation).
 
If treatment interruption is longer than 28 days, the subject will be discontinued from IP (refer to Section 7.2 for handing IP discontinuation)..

AST or ALT > 5 times the institutional ULN	Interrupt AL101 until resolution to \leq Grade 1 and then decrease dose to 4 mg QW for first episode and to 2.4 mg QW for second episode.	Interrupt AL101 until resolution to \leq Grade 1 and then decrease dose to 2.4 mg QW.

Dose Modification Criteria for AL101 -Related Adverse Events	AL101 modification at next dose	
	Dose 6 mg QW	Dose 4 mg QW
	
Refer to Section 6.4.3 for hepatic function abnormalities and Figure 2 for drug-induced liver toxicity management.
 
If treatment interruption is longer than 28 days, the subject will be discontinued from IP (refer to Section 7.2 for handing IP discontinuation)..
	
Refer to Section 6.4.3 for hepatic function abnormalities and Figure 2 for drug-induced liver toxicity management.
 
If treatment interruption is longer than 28 days, the subject will be discontinued from IP (refer to Section 7.2 for handing IP discontinuation)..

Hy's law cases (e.g. drug induced liver injury; DILI) as defined in Section 6.4.3.1 and assessed by the investigator and Sponsor	Immediately discontinue IP (refer to Section 7.2 for handing IP discontinuation)	Immediately discontinue IP (refer to Section 7.2 for handing IP discontinuation)
Triglyceride Grade 3 elevations that persist after 4 weeks of medical management	
Interrupt AL101 until resolution to \leq Grade 1 and then decrease dose to 4 mg QW for first episode and to 2.4 mg QW for second episode.
 
If treatment interruption is longer than 28 days, the subject will be discontinued from IP (refer to Section 7.2 for handing IP discontinuation)..
	
Interrupt AL101 until resolution to \leq Grade 1 and then decrease dose to 2.4 mg QW.
 
If treatment interruption is longer than 28 days, the subject will be discontinued from IP (refer to Section 7.2 for handing IP discontinuation).

Infusion-related reaction	For dose modification and management of infusion-related reactions, refer to Section 6.4.1.	For dose modification and management of infusion-related reactions, refer to Section 6.4.1.
Any other AL101-related Grade 3 nonhematologic adverse event except electrolyte abnormalities that may be managed with supplements	
Interrupt AL101 until resolution to \leq Grade 1 and then change dose regimen to 6 mg 2 weeks on / 1 week off for the first episode.
 
Decrease AL101 dose to 4 mg QW for second episode and to 2.4 mg QW for third episode.
 
If treatment interruption is longer than 28 days, the subject will be discontinued from IP (refer to Section 7.2 for handing IP discontinuation)..
	
Interrupt AL101 until resolution to \leq Grade 1 and then decrease dose to 2.4 mg QW.
 
If treatment interruption is longer than 28 days, the subject will be discontinued from IP (refer to Section 7.2 for handing IP discontinuation).

Grade 4 non-hematologic AEs including Grade 4 non-	Permanently discontinue from IP (refer to Section 7.2 for handing IP discontinuation).	Permanently discontinue from IP (refer to Section 7.2 for handing IP discontinuation).

Dose Modification Criteria for AL101 -Related Adverse Events	AL101 modification at next dose	
	Dose 6 mg QW	Dose 4 mg QW
hematologic lab abnormalities lasting \geq 72 hours		

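### At 6 mg QW, the Section 6.4 text and two rows of Table 3 prescribe different dose steps for related Grade 3 diarrhea and other Grade 3 non-hematological events, with no precedence rule

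*Combined protocol and SAP*

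**What the plan says.** Section 6.4 opens by pointing to the table: "Dose modification associated with AL101 is described below in" Table 3. It then sets a general rule. The causality assessment "will be used by the investigator for assessing drug-related non-hematological Grade 3" events, other than isolated electrolyte abnormalities without symptoms that are reversed within 48 hours, "and hematological Grade 4 toxicities". The action is: "If there is a relationship to the drug, this will lead to a 1 dose level reduction for AL101". The paragraph makes no exception for a first episode. It adds: "Re-escalation of the dose following a dose reduction is not allowed".

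Table 3, in the 6 mg QW column of the Grade 3 diarrhea row, says: "Change dose regimen to 6 mg 2 weeks on / 1 week off for the first episode". It continues: "Decrease AL101 dose to 4 mg QW for second episode and to 2.4 QW mg for third episode". The catch-all row for other related Grade 3 nonhematologic events gives the same three steps. The neutropenia row is limited by duration: "Grade 4 neutropenia lasting" 7 days or more.

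Two other rows bear on GI bleeding. Related Grade 2 GI bleeding at 6 mg QW goes to 4 mg QW at the first episode and 2.4 mg QW at the second. The Grade 3 or 4 row requires permanent discontinuation but names only gastric hemorrhage.

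**The concern.** Two instructions in one section give a site different doses for the same event in the same subject. One reduces the infusion to 4 mg; the other keeps 6 mg and drops every third week. Nothing states which prevails.

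The events concerned are the ones that raised the dose question for this drug. Section 4.3 reports dose-limiting toxicities in 4 of the 14 subjects (4 + 10) treated at 6 mg QW in the first-in-human study: two with Grade 3 diarrhea, one with Grade 3 vomiting and lipase elevation, and one with a Grade 3 large intestinal ulcer. The first two fall in the diarrhea row. The other two fall in the catch-all row, unless the ulcer is managed as colitis.

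Infusion size also matters on the sponsor's own argument, since Section 4.3 reports a considerably larger Hes1 and Hes4 reduction at 6 mg than at 4 mg. At stake are consistent dosing across sites and a clear safety rule.

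**Working it through.** Section 6.4 does not define its dose levels. I take them from the Table 3 steps: 6, 4 and 2.4 mg QW. Planned dose is counted over 12 weeks after restart, the common multiple of the 3-week on/off pattern and the 4-week cycle, with no missed infusions.

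| Related Grade 3 diarrhea or catch-all event, starting at 6 mg QW | 6.4 text | Table 3 |
|---|---|---|
| After 1st episode | 4 mg QW: 12 × 4 = 48 mg | 6 mg, 2 on / 1 off: 12 × 2/3 = 8 infusions; 8 × 6 = 48 mg |
| After 2nd episode | 2.4 mg QW: 12 × 2.4 = 28.8 mg | 4 mg QW: 12 × 4 = 48 mg |
| After 3rd episode | no level defined below 2.4 mg QW | 2.4 mg QW: 28.8 mg |

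At the first episode the totals agree and the infusion differs (4 against 6 mg). At the second the difference is 48 − 28.8 = 19.2 mg, and 48 / 28.8 = 1.67, so Table 3 gives 67% more.

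Where the two sources agree:
- The AST/ALT row (above 5 times ULN) and the persistent Grade 3 triglyceride row go to 4 mg QW and then 2.4 mg QW, the same dose steps as the text.
- In the 4 mg column, related Grade 3 diarrhea and catch-all events go to 2.4 mg QW, one level down.

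The hematological half of the sentence differs from the table in two ways. A related Grade 4 neutropenia shorter than 7 days requires a reduction under the text but does not meet the Table 3 row. Other Grade 4 hematological toxicities, such as anemia, have no Table 3 row, so the text is their only dose rule.

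GI bleeding, if Table 3 governs and gastric is read literally: a related Grade 3 non-gastric bleed that is not managed as colitis, and has no Grade 3 or higher thrombocytopenia, matches no bleeding row and falls to the catch-all. Its steps at 6 mg QW are 6 mg 2 on / 1 off, 4 mg QW, 2.4 mg QW. A Grade 2 GI bleed steps to 4 mg QW, then 2.4 mg QW. The higher grade reaches each reduced level one episode later.

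**The case against.** The best defence is that Table 3 plainly governs. Section 6.4 refers to it at the outset, it is specific by row, grade and episode, and the amendment rationale places the on/off regimen ahead of dose reduction. Two weeks on / 1 week off averages 12 mg over 3 weeks, or 4 mg a week, so it could be called one level down. For diarrhea, Section 6.4.2 allows lower frequency as well as lower dose and leaves room for clinical judgment.

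Much of this stands. Table 3 is probably what is meant, the first-episode totals are equal, and some variation between sites in handling diarrhea is expressly allowed. It does not remove the conflict:
- The text's rule is mandatory and has no visible sign of being obsolete, because the AST/ALT and triglyceride rows still follow it.
- Table 3 words the regimen change and the dose decrease as separate steps, as does the amendment rationale.
- That rationale names Grade 2 or 3 diarrhea and Grade 2 colitis, not the catch-all row, so intent there is less certain.
- The discretionary wording in 6.4.2 does not say which of the two fixed rules applies.

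Three stronger readings are tempting and are not supported. First, a reader might infer that the first choice is permanent under either source. The re-escalation bar follows a dose reduction, so only the move to 4 mg is locked; a subject on 2 on / 1 off can still step down. Second, a reader might project earlier event rates onto 67 subjects and treat the result as the number given a different total dose. Such counts are of subjects with any event, whereas totals diverge only from the second. Third, a reader might take the bleeding sequence as an established inversion of safety rules. It disappears if the text governs, if gastric meant gastrointestinal, or if the bleed is managed as Grade 3 colitis, which stops treatment. Section 7.2 also requires Medical Monitor approval before restart after a serious related reaction, though it sets no dose.

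**Conclusion.** The inconsistency is real and should be fixed. It is confined to the 6 mg QW dose for the diarrhea and catch-all rows, plus the Grade 4 neutropenia threshold. It changes the infusion dose from the first episode and the planned total from the second (28.8 against 48 mg per 12 weeks). That comparison rests on reading a level as 6, 4 or 2.4 mg QW and on uninterrupted dosing after restart. How many subjects would have a second episode cannot be derived from the documents.

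The bleeding point is minor and conditional, and its frequency cannot be sized. Sample size, error rates and the definition of the primary endpoint are unaffected.

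**What to change.** (a) Replace the general sentence in Section 6.4 with: *Related Grade 3 non-hematological and Grade 4 hematological toxicities listed in Table 3 (Table 4 for colitis) are managed as stated there, including the first-episode regimen change at 6 mg QW and the 7-day threshold for Grade 4 neutropenia; any other related Grade 4 hematological toxicity leads to a 1 dose level reduction.* The last clause is needed so that events such as Grade 4 anemia keep a dose rule. The sponsor should first confirm that the regimen change was intended for the catch-all row.

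(b) Give the two GI bleeding rows the same anatomical scope. Extending the Grade 3 or 4 row to all GI hemorrhage would make discontinuation mandatory for related Grade 3 non-gastric bleeds at both doses. At minimum, give those bleeds steps no milder than the Grade 2 row. That leaves the 4 mg column unchanged. At 6 mg QW it lowers the infusion dose after a first such bleed, and lowers the planned total by 19.2 mg per 12 weeks only after a second.

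(c) Correct the colitis referral in the Grade 2 GI bleeding row from 6.4.3.1, which covers drug-induced liver injury, to 6.4.4.

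The edits are short. Because (a) and (b) both change safety rules, they need a protocol amendment with IEC/IRB approval under Section 10.1.3.1. They add no procedures and leave the sample size as it is.
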